## 1 Study Summary

#### 1.1 Hypotheses

The hypotheses of this multicenter cohort study of in-hospital intensive care unit pediatric cardiac arrest in CPCCRN are:

- 1. Pediatric CPR events with average arterial diastolic blood pressures  $\geq$  30mmHg will be associated with a higher rate of ROSC.
- 2. Pediatric CPR events with average  $ETCO_2 \geq 20$ mmHg will be associated with a higher rate of ROSC.
- 3. Arterial diastolic blood pressure and  $ETCO_2$  during CPR, as surrogates of perfusion will be associated with survival outcomes.
- 4. Chest compression measurements (depth, rate, and fraction) during CPR will be associated with arterial diastolic blood pressure,  $ETCO_2$ , and survival outcomes.

The hypothesis concerning chest compression measurements will only be assessed at participating sites that are able to use a quality of CPR measurement device during CPR.

#### 1.2 Specific Aims

This project includes the following Specific Aims:

- Specific Aim 1. Assess the association between arterial diastolic blood pressures during CPR and the rate of ROSC  $\geq 20$  minutes.
- **Specific Aim 2.** Assess the association between  $ETCO_2$  during CPR and the rate of ROSC  $\geq 20$  minutes.
- Specific Aim 3 (exploratory). Obtain evidentiary support associating arterial diastolic blood pressure and  $ETCO_2$  measurements during CPR with survival outcomes.
- Specific Aim 4 (Optional). Obtain evidence associating chest compression measurements (depth, rate, and fraction) during CPR with arterial diastolic blood pressure,  $ETCO_2$ , and survival outcomes.

Specific Aim 4 will only be carried out at participating sites that are able to use a quality of CPR measurement device during CPR.

### 1.3 Subject Eligibility, Accrual and Study Duration

**Inclusion criteria:** A CPR event will be eligible for study enrollment if the answer to both of the following questions is YES:

- 1. Did the patient receive chest compressions for  $\geq 1$  minute in the PICU or the CICU?
- 2. Is the patient  $\geq$  37 weeks gestational age and < 19 years of age?

A CPR event will be eligible for assessing quality of chest compression during CPR in participating institutions if a device (e.g., ZOLL R-series, Philips MRx, Physiocontrol LIFEPAK 20e) is FDA cleared for use according to the age of the patient.

**Exclusion Criteria:** A CPR event will be ineligible for study enrollment if the answer to any of the following questions is NO:

- 1. Did the patient have either an arterial line or  $ETCO_2$  monitor in place at the time of chest compressions?
- 2. Were there use able waveform data available from either the arterial line or  $ETCO_2$  monitor?
- 3. At the time the CPR Event began, was the patient free from ECMO therapy?

Based upon pilot CPCCRN data, approximately 260 CPR events are expected to occur on an annual basis, resulting in approximately 130 events with eligible arterial data (Please see Table 1: PICqCPR Pilot Data). We will plan a 3 year study with a targeted enrollment of 390 CPR Events.

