As this study is considered exploratory in nature, a two-sided test with Type I error of 0.05 will be performed separately for each of the two hemodynamic parameters, and again separately for the Aim 3 evaluations.

Beyond this basic analysis, we will examine alternative cut points for the two hemodynamic parameters as predictors of ROSC, and more generally assess their overall association with ROSC, via the use of receiver operating characteristic curves. This approach may determine alternative hemodynamic parameter cut points strongly associated with ROSC; utility of criteria determined in this fashion will require validation in future studies.

It will also be important to determine the association of hemodynamic parameters with outcomes, adjusted for patient risk profile and event characteristics up until the time of arrest. For binary outcomes such as ROSC and survival, multivariable regression models will be used to assess this association. As ROSC and other favorable outcomes are not expected to be rare events, we will analyze this prospective study by estimating the relative risk of an event rather than the odds ratio, using the modified Poisson regression approach. As the number of potential adjustment variables is large relative to the number of events, factors for adjustment will be selected from those showing relatively strong statistical association with each outcome. Specific modeling strategies will be documented in more detail in the Statistical Analysis Plan.

While we will compare absolute values of PCPC and FSS between patient subgroups defined by hemodynamic and other parameters, we also expect to dichotomize these outcome measures for similar analyses. An exploratory outcome measure of interest will be "survival with favorable outcome," which may be defined as discharge alive without substantial worsening of PCPC/FSS relative to pre-event status and discharge alive with PCPC 1-3.

For Specific Aim 4, we will describe the quality of chest compression measurements (compression depth, rate, and fraction of time compressed) during CPR, and measure association with arterial diastolic blood pressure,  $ETCO_2$ , and survival outcomes.

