#### 5.1 Sample Size

Based upon pilot CPCCRN data, approximately 260 CPR events are expected to occur on an annual basis, resulting in approximately 130 events with eligible arterial data (See Table 1: PICqCPR Pilot Data).

Site:	#wks:	#CPR events:	Arterial Catheter at time of CPR:	Eligible Arterial Catheter Data:	Annual Eligible CPR Events with Arterial Catheter Data:
СНОМ	20	13	7(54%)	5(38%)	13
CHOP	20	9	3(33%)	3(33%)	7
CNMC	17.1	21	14(67%)	11(52%)	33
CHLA	19.3	16	8(50%)	8(50%)	21
UCLA	20	9	7(78%)	5(56%)	13
MICH	18	10	7(70%)	6(60%)	17
PHNX	20	11	6(55%)	6(55%)	15
UPMC	20	8	6(75%)	5(63%)	13
Totals:	n/a	97	58(60%)	49(51%)	132

Table 1: PICqCPR Pilot Data
-----------------------------

Further, based upon CHOP limited preliminary data, we can assume that approximately 60% of pediatric CPR events will have average event arterial diastolic blood pressures exceeding 30 mmHg. We must also assume that 30% of events with average arterial diastolic blood pressures less than 30 mmHg will still obtain ROSC, based upon large registry data. Using these conservative estimates, in just one year, we will have

more than 90% power to detect a doubling in likelihood of ROSC ( $\sim 60\%$  ROSC rate) when the event average diastolic pressure exceeds 30 mmHg. However, in light of the higher number of subjects needed to determine if the ROSC rate associated with higher arterial diastolic pressures would be 50% more (a very important clinical effect), 3-4 years may be necessary for more than 80% power to detect a significant effect in the setting of a 50% increase. Because this will be the first study to assess the association of CPR hemodynamics with outcomes in children, we will plan a 3 year study with 390 CPR events.

For additional examples of estimated sample sizes needed for substantial power when these parameters are varied, see Table 2: Sample Size Estimates. (These estimates are approximate, as correlation between multiple events occurring in the same patient may slightly affect power). We do not expect this study to have high power for detecting a significant association between hemodynamic parameters and survival, as effect on patient survival outcomes is expected to be substantially moderated relative to beneficial effect on acute ROSC.

Table 2:	Sample	Size	Estimates
----------	--------	------	-----------

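### The target of 390 CPR events is in the wrong unit: eligibility accepts arterial or ETCO2 data, but 390 is three years of arterial-data events, so Aim 1's power margin depends on how accrual ends

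*Protocol*

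**What the plan says.** **Who is enrolled.** Protocol section 1.3 screens on the monitor, "Did the patient have either an arterial line or" an ETCO2 monitor, and then on the signal, "Were there use able waveform data available from either the arterial line or" the ETCO2 monitor. One usable signal of either kind is enough.

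**What is expected.** Section 1.3 says that "approximately 260 CPR events are expected to occur on an annual basis". Section 5.1 repeats this figure and continues: "resulting in approximately 130 events with eligible arterial data". Table 1 gives the pilot basis: 97 CPR events, of which 49 (51%) had eligible arterial catheter data.

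**The target.** Section 1.3 says "We will plan a 3 year study with a targeted enrollment of 390 CPR Events", and section 5.1 says "we will plan a 3 year study with 390 CPR events". Neither sentence says which monitor the 390 events must have.

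**The power case.** Section 5.1 and Table 2 size only the comparison of ROSC between DBP at or above 30 mmHg and below it. They assume that "approximately 60% of pediatric CPR events will have average event arterial diastolic blood pressures exceeding 30 mmHg" and that 30% of the low-pressure events reach ROSC. For a 50% relative increase, Table 2 needs 368 events for 80% power and 483 for 90%. For a doubling at 90% power it needs 130. Section 5 sets the level: "a two-sided test with Type I error of 0.05 will be performed separately for each of the two hemodynamic parameters".

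**The concern.** An event with ETCO2 data only is enrolled and counts toward 390, but it contributes nothing to the DBP comparison that justifies 390. Under the either-monitor rule, the three-year duration and the count of 390 agree only if ETCO2-only events are close to zero. The protocol gives no reason to expect that: Aim 2 studies ETCO2 in its own right, and 48 of the 97 pilot events lacked eligible arterial data.

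At stake is whether a reported target means what it appears to mean. As written, a report could say that the target was met while the number of events evaluable for Aim 1 fell short of the number that the power statement needs. No minimum number of arterial events is set anywhere in the protocol.

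**Working it through.** **Inputs.** All are from the protocol unless marked: two-sided alpha 0.05 (section 5); ROSC 30% when DBP is low, and 60% of events with high DBP, so a ratio k = 1.5 (section 5.1); a 50% relative increase, so 45%; 130 arterial-data events and 260 CPR events per year (sections 1.3 and 5.1). The share of enrolled events with ETCO2 only is **not given**. It is treated as an assumption and varied.

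**Step 1. Where 390 comes from.** 3 × 130 = 390. Annualising Table 1 site by site (52 × events ÷ weeks, summed) gives 265.9 CPR events and 134.7 arterial-data events per year, in line with the stated 260 and 130.

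**Step 2. Reproduce Table 2 (60% row, 50% effect, 80% power).** With p1 = 0.30, p2 = 0.45, d = 0.15 and pooled p̄ = (0.30 + 1.5 × 0.45)/2.5 = 0.39:

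- Low-DBP group, uncorrected: m = [1.96·√(p̄(1−p̄)(1+1/k)) + 0.842·√(p1(1−p1) + p2(1−p2)/k)]² / d² = (1.234 + 0.515)²/0.0225 ≈ 136.0. Total = 2.5 × 136.0 = 340.1.
- Continuity-corrected: m′ = (m/4)·[1 + √(1 + 2(1+1/k)/(m·d))]² ≈ 146.9. Total = 2.5 × 146.94 = 367.4.

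The corrected total matches the stated 368; the uncorrected one does not. At 90% power the corrected total is 480.3, against 483 stated. The corrected formula reproduces 16 of Table 2's 18 cells, and the other two are about 2 events off. It is therefore taken as the protocol's method.

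**Step 3. Power at 390 arterial events.** Power = Φ[(d − ½(1/n1 + 1/n2) − 1.96·se0)/se1], with n1 = 156 and n2 = 234. Here se0 = √(0.39 × 0.61 × (1/156 + 1/234)) = 0.0504 and se1 = √(0.21/156 + 0.2475/234) = 0.0490. So Φ[(0.1447 − 0.0988)/0.0490] = Φ(0.935) = 82.5%. Without the correction it is 85.2%.

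**Step 4. The margin.** 390 − 368 = 22 events, and 22/390 = 5.6%. Against the uncorrected 340 it is 50 events, and 50/390 = 12.8%.

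**Step 5. If 390 counted events of either kind.** Power for 30% versus 45%:

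| ETCO2-only among 390 | Arterial events | Power, corrected | Power, uncorrected |
|---|---|---|---|
| 0 | 390 | 82.5% | 85.2% |
| 39 (10%) | 351 | 78.0% | 81.2% |
| 78 (20%) | 312 | 72.5% | 76.5% |
| 130 (33%) | 260 | 63.7% | 68.5% |
| 195 (50%) | 195 | 49.8% | 55.9% |

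The last row is a bound. It assumes that all of the roughly 260 yearly CPR events are otherwise eligible and that every one without arterial data has usable ETCO2.

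**Step 6. Count against duration.** Let q be the share of the 130 non-arterial events per year that have usable ETCO2. Eligible events per year are then 130(1 + q).

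| q | Eligible per year | Years to reach 390 | Arterial events in those 390 | Enrolled over 3 years | Arterial events over 3 years |
|---|---|---|---|---|---|
| 10% | 143 | 2.7 | about 355 | 429 | 390 |
| 50% | 195 | 2.0 | 260 | 585 | 390 |
| 100% | 260 | 1.5 | 195 | 780 | 390 |

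The two readings of the target diverge as soon as q is above zero. Only the count-based reading loses arterial events.

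**Step 7. The doubling effect (30% versus 60%).** At 130 arterial events, corrected power is 90.1%, which reproduces the protocol's one-year statement. At 195 (n1 = 78, n2 = 117, p̄ = 0.48) it is Φ[(0.2893 − 1.96 × 0.0730)/0.0689] = Φ(2.12) = 98%. This claim is safe in every scenario above.

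**The case against.** A reader might infer that Aim 1 will end up below 80% power. The documents do not support that, for four reasons.

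- **No closing rule at 390.** Both target sentences attach 390 to a three-year study. The consent-waiver argument in section 7 rests on capturing every eligible event in the study period, which suggests accrual by time. A full three years keeps about 390 arterial events and 82.5% power.
- **Context hints at the unit.** In section 1.3 the target directly follows the arterial-data rate, and in section 5.1 it closes a discussion of DBP. The likely intent is 390 arterial events with the qualifier dropped.
- **The shortfall needs an unknown.** The ETCO2-only share is not stated, and the 195-event case is a bound, not a forecast.
- **The 80% figure is hedged.** Section 5.1 says that three to four years may be needed for the 50% effect and calls its sample sizes approximate. Section 5 calls the study exploratory. The firmer claim, more than 90% power for a doubling, survives throughout.

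All four points stand, and they make the loss of power conditional. They do not remove the mismatch. The text enrols on one definition and justifies its target on a narrower one, and the reader has to supply both the missing qualifier and the rule that ends accrual.

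**Conclusion.** The enrolment target is stated in the wrong unit. It counts events eligible by either monitor, while its derivation and its power support concern events with arterial data only. That much follows from the text without any outside figure.

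The effect on Aim 1 is conditional. It arises only if accrual is judged complete at 390 events of either kind **and** more than about 5.6% of them are ETCO2-only (12.8% without continuity correction). Power for 30% versus 45% ROSC is then below 80%: 78% at 351 arterial events, 73% at 312, 64% at 260 and 50% at the floor of 195. If enrolment runs the full three years at the stated rates, Aim 1 keeps about 390 arterial events and 82.5% power.

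These figures use the protocol's 60% prevalence and 30% baseline ROSC, and they ignore within-patient correlation. Severity is moderate: the protocol's main size figure is ambiguous and its margin is thin, but no loss of power is established.

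**What to change.** In sections 1.3 and 5.1:

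1. State the target as about 390 CPR events with evaluable arterial waveform data, expected over 3 years.
2. State that total enrolment under the either-monitor rule will be larger. On the protocol's rates it would be about 429 to 780 if 10% to 100% of the non-arterial events have usable ETCO2.
3. State that the three-year period or the arterial count, and not the total count, ends accrual.

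If 390 in total is truly intended, keep it and restate the Aim 1 power as a range over the expected number of arterial events.

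**Cost.** The wording change is a sentence or two in each section, and the planned duration does not change. The first option means abstracting more ETCO2-only records, at the extreme twice as many enrolled events as now stated. That matters because section 5 already cites limited resources for data collection, although the extra records serve Aim 2. The alternative adds no data collection but gives a less favourable power statement.

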# 2 Background and Significance

Cardiac arrests in children are a major public health problem. Thousands of children in the USA are treated in pediatric intensive care units (PICUs) with cardiopulmonary resuscitation (CPR) each year for sudden in-hospital cardiac arrest. Neurological outcomes following these in-hospital PICU CPR events are often abnormal. As children with neurological deficits following in-hospital CPR are a major burden for families and society, improving neurological outcomes through superior blood flow during CPR is an important clinical goal. Studies in animals have established that survival following CPR for cardiac arrest depends on attaining adequate myocardial blood flow. Myocardial perfusion pressure, also known as coronary perfusion pressure (CPP) (determined mathematically as arterial diastolic pressure minus right atrial diastolic pressure) is the primary determinant of myocardial blood flow.

Limited adult data confirm the importance of attaining adequate coronary perfusion pressure for survival from CPR. However, there is a paucity of published hemodynamic data during CPR in children, so the relationship between hemodynamics during CPR and outcomes has not been rigorously evaluated in children and is a major knowledge gap.

Similarly, end-tidal carbon dioxide  $(ETCO_2)$  has also been used as a marker of CPR quality/intra-arrest hemodynamics (i.e., pulmonary blood flow). Animal studies have established that  $ETCO_2$  during CPR correlates with cardiac output and survival. Also, adult studies have confirmed that attaining adequate  $ETCO_2$  is necessary for survival. Yet again, published pediatric data associating  $ETCO_2$  during CPR with hemodynamics and survival outcomes is minimal. Currently the American Heart Association (AHA) recommends monitoring of  $ETCO_2$  during pediatric CPR, using extrapolated data from animals and adults with little data collected from actual children.

Limited pediatric data describe the quality metrics of the delivery of CPR (e.g., depth of compression, rate, and fraction of chest compression) during in-hospital resuscitation, nor the association of chest compression characteristics with hemodynamic and survival outcomes.

Therefore, the objective of this investigation is to obtain evidentiary support to associate hemodynamics during CPR (arterial diastolic pressure and  $ETCO_2$ ) with outcomes in those children who suffer an arrest within CPCCRN PICUs and CICUs. In addition, at participating sites that are able to use a quality of CPR device during CPR, measurements will be obtained to describe the characteristics of chest compressions (depth, rate, and fraction of compression) observed during CPR events.

## 3 Study Design

The overall objective of the Pediatric Intensive Care Quality of CPR (PICqCPR) Study is to measure high-fidelity hemodynamic data during CPR in CPCCRN intensive care units, and to evaluate the relationship between these parameters and important clinical outcomes. The PICqCPR Study is a multicenter cohort study of in-hospital intensive care unit pediatric cardiac arrests within the CPCCRN network. The Pediatric Intensive Care Unit (PICU) and Cardiac Intensive Care Unit (CICU) are the only two locations within clinical centers that will be used for subject accrual.

For the purposes of this study, CPR is defined as administration of chest compressions for at least one minute. Return of circulation will be recorded, regardless of whether ECMO was utilized or not. The outcome metric for successful CPR is return of spontaneous circulation (ROSC) for at least 20 minutes duration. Repeat chest compression episodes for the same subject are eligible for inclusion. If a subject sustains ROSC for at least 20 minutes after chest compressions end, and then arrests again, it is considered a separate and new event.

## 4 Data Collection and Procedures

Note that the specific questions and choice sets that are included below may not represent the final data collection implemented in the electronic data capture system. If substantively new data elements are added to the study, this protocol will be amended.

### 4.1 Patient Characteristics

- Date of Birth
- Sex
- Race/Ethnicity
- Height & Weight
- Baseline Pediatric Cerebral Performance Category (PCPC)
- Baseline Functional Status Scale (FSS)
- Was there an out-of-hospital cardiac arrest that led to this hospital admission?
- Date and time of hospital admission
- Date and time of ICU admission
- Location of event (PICU or CICU)
- Illness Category:
  - Medical cardiac
  - Medical non-cardiac
  - Surgical cardiac
  - Surgical non-cardiac
  - Trauma
- Pre-existing conditions (at time of CPR event):

- Respiratory insufficiency
- Hypotension
- Congestive heart failure
- Pneumonia
- Sepsis
- Trauma
- Renal Insufficiency
- Malignancy
- Congenital Heart Disease
  - If yes, single ventricle?
    - If yes, specify anatomy at time of CPR event:
      - Preoperative
      - Norwood with modified BT Shunt
      - Norwood with Sano Modification
      - Bi-directional Glenn (Hemi-Fontan)
      - Fontan

## 4.2 CPR Event Characteristics

- Date and time of start of chest compressions
- Interventions in place at time of event:
  - Vascular Access
  - Arterial catheter
  - Central venous catheter
  - Vasoactive infusion
  - Invasive mechanical ventilation
  - *ETCO*2 monitoring
  - Non-invasive ventilation
- Immediate cause of CPR Event:
  - Hypotension
  - Respiratory decompensation
  - Arrhythmia (VF, VT, SVT)
  - Cyanosis without respiratory decompensation
- Was it a witnessed CA?
- First documented rhythm requiring CPR:
  - VF
  - VT
  - Pulseless electrical activity [PEA]

- Asystole
- Bradycardia with pulses
- Open or closed sternum at onset of CPR event
- Date and time sternum opened during CPR event
- Time of first shockable rhythm
- Time of first attempted defibrillation for shockable rhythm
- Time of first administration of a vasopressor medication bolus
- Pharmacologic interventions during CPR:
  - Epinephrine
    - What was the total number of epinephrine doses?
  - Atropine
  - Calcium
  - Sodium Bicarbonate
  - Vasopressin
  - Amiodarone
  - Lidocaine
  - Fluid Bolus
  - Other (Specify)
- Date and time of end of chest compressions
- Outcome of CPR Event:
  - $ROSC \ge 20$  minutes
  - Transition to ECMO with ROSC <20 minutes
  - Transition to ECMO without ROSC
  - Died

## 4.3 Hemodynamic Variables

The following variables will be collected once every minute for a maximum of ten minutes prior to the beginning of chest compressions:

- Heart rate
- Systolic arterial blood pressure
- Diastolic arterial blood pressure
- Mean arterial blood pressure
- $ETCO_2$
- Central venous pressure/Right atrial pressure
- Pulse oximetry  $SpO_2$

Waveforms of the following variables will be provided throughout the duration of the first 10 minutes of chest compressions, as well as the last minute prior to the end of chest compressions.

- Arterial diastolic pressure
- Arterial systolic pressure
- Central venous pressure/Right atrial pressure
- $ETCO_2$
- Electrocardiogram (bedside monitor)
- Plethysmography (bedside monitor)
- Pulse oximetry  $SpO_2$
- Actual chest compressions provided per minute

The following variables will be collected once every five minutes for the first 20 minutes after chest compressions have ended:

- Heart rate
- Systolic arterial blood pressure
- Diastolic arterial blood pressure
- Mean arterial blood pressure
- $ETCO_2$
- Central venous pressure/Right atrial pressure
- Pulse oximetry  $SpO_2$

